Effects of Reparel™ Knee Sleeve on Knee Osteoarthritis

Study Protocol & Statistical Analysis Plan

NCT04743921

April 4th, 2022

[name], Principal Investigator
University of Alabama at Birmingham
Birmingham, AL 35294

Objectives:

Osteoarthritis (OA) is one of the most prevalent musculoskeletal ailments worldwide. Numerous conservative therapies exist, but evidence for such treatments remains conflicting. Recently, there has been growing interest surrounding bioactive sleeves for managing knee arthritis. However, the literature on their efficacy for relieving pain and improving function in the setting of knee OA is limited. Therefore, we sought to investigate the effect of a bioactive sleeve on patient reported outcome measures (PROMs) in a small cohort of OA patients.

Methods:*Patient Recruitment and Inclusion*

Following institutional review board approval and registration with ClinicalTrials.gov, the authors will prospectively follow a series of patients at an outpatient orthopaedic sports medicine clinic between February and July 2021. Patients who opt for non-operative management of knee OA will be informed and consented for the study. Patients will be included if they have radiographic evidence of knee OA, no previous surgery on the symptomatic knee, no corticosteroid knee injection within 3 months of the study, and agree to abstain from a knee injection during the 3 month study period. Patients will be excluded if diagnosed with bilateral symptomatic knee OA, had previously undergone knee surgery, were grossly unstable on physical examination, or had a history of knee malignancy. Patients will be instructed to wear the sleeve (Reparel, Chico, CA) as long as tolerated throughout the day and to refrain from modifying usual activities and diet.

Patient Assessment

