Participants will be asked to complete the following patient reported outcome measures (PROM): the University of California, Los Angeles Activity Score(UCLA),¹¹ which measures current activity level; the Lysholm Score(LKS),¹² which measures joint stability and function; the Oxford Knee Score (OKS),¹³ which measures knee related health status; the Knee Injury and Osteoarthritis Outcome Score (KOOS),¹⁴ which assesses difficulties with physical activity; the Single Assessment Numeric Evaluation (SANE),¹⁵ which assesses perceived functional level; and the Visual Analog Scale (VAS),¹⁶ which assesses perceived pain level. These surveys will be administered at the initial visit and subsequently over the phone at 2 weeks, 6 weeks, and 3 months later. Patients will also be asked about average daily sleeve usage, product satisfaction, and complaints/issues.

Osteoarthritis Severity Assessment

OA severity will be defined by clinical radiographic imaging using the Kellgren-Lawrence (KL) classification system at the baseline clinical visit.¹⁷ The radiographs will be read and graded by a sports medicine fellowship trained orthopedic surgeon.

Statistical Analysis

Statistical analysis will be performed using SPSS (IBM SPSS Statistics for Macintosh, Version 27.0. Armonk, NY: IBM Corp). Mann-Whitney test will be used to compare baseline demographics between male and female patients. Wilcoxon Signed-Rank test will be used to compare baseline PROMs and hours of sleeve use with those at 2 week, 6 week, and 3 month time points. Kruskal Wallis test will be performed to evaluate differences in PROs between the four time points. When analyzing PROs between

time points within groups with differing population counts, only patient scores that are available between groups will be analyzed. Significance will be set to an alpha of 0.05.

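### As written, hours of sleeve use are tested against baseline, where the test is degenerate or impossible if the sleeve was not worn before; no other reference time is given

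*Combined protocol and SAP*

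**What the plan says.** One sentence in the Statistical Analysis section covers sleeve hours. It assigns the Wilcoxon signed-rank test to "compare baseline PROMs and hours of sleeve use with those at 2 week, 6 week, and 3 month time points". The other rules about time points do not reach hours: "Kruskal Wallis test will be performed to evaluate differences in PROs between the four time points", and the rule for unequal counts, under which "only patient scores that are available between groups will be analyzed", is introduced as a rule for PROs. Alpha is 0.05. Sidedness is not stated, nor whether p-values will be exact or approximate.

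Patient Assessment schedules the PROM surveys at the first visit and at three later telephone contacts. Usage has a sentence of its own with no time attached: "Patients will also be asked about average daily sleeve usage, product satisfaction, and complaints/issues".

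Under Patient Recruitment and Inclusion, "Patients will be instructed to wear the sleeve (Reparel, Chico, CA) as long as tolerated throughout the day". The document does not say when the sleeve is issued, does not mention earlier wear and does not exclude it. It gives no sample size. The aim under Objectives is framed in terms of PROMs: "we sought to investigate the effect of a bioactive sleeve on patient reported outcome measures (PROMs) in a small cohort of OA patients".

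**The concern.** A signed-rank test needs a defined pair of measurements for each patient. For PROMs the pair is clear: baseline and a follow-up call. For hours, the same sentence carries over a baseline value that probably has no useful content, because patients receive the sleeve as the study intervention. Wear is also left to tolerance, so the usage answers are the only record of exposure.

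Two questions matter to someone reading the PROM results: how much the sleeve was worn, and whether wear fell away over the 3 months. A test against zero answers neither. A small p-value would look like evidence of good adherence when it shows only that several patients wore the sleeve at all. If baseline was not meant for hours, the reference call is left open and could be chosen after the data are seen.

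**Working it through.** There is no stated figure to reproduce. The check follows the two ways of reading the sentence.

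**Inputs.** Test and time points: Statistical Analysis. Alpha 0.05: same section, two-sided assumed. Baseline hours zero or unrecorded: inferred from the sleeve being the intervention, and conditional on no earlier wear. Number of patients: not given, so m (patients reporting any use at a call) is varied.

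**Reading 1: baseline governs both PROMs and hours.**

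*Baseline hours zero.* Every non-zero difference is positive, so the rank sum is at its maximum. Only one of the 2^m equally likely sign patterns gives that maximum, and doubling for two sides gives p = 2 × 0.5^m.

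| m | exact two-sided p |
|---|---|
| 5 | 2 × 0.03125 = 0.0625 |
| 6 | 2 × 0.015625 = 0.031 |
| 10 | 2 × 0.000977 = 0.0020 |

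Hours worn do not enter. Ten patients at 1, 2, …, 10 h a day (median 5.5 h) and ten at 0.1, 0.2, …, 1.0 h (median 0.55 h) both give W+ = 10 × 11 / 2 = 55 and p = 0.0020. Non-wearers do not enter either, because the standard procedure drops zero differences. With 20 patients (assumed), of whom 6 report some use and 14 none, m = 6 and p = 0.031, although 14/20 = 70% report no use.

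If normal-approximation p-values are reported, the threshold depends on the continuity correction. Without ties, z = [m(m+1)/4] / √[m(m+1)(2m+1)/24]. If all patients report the same hours, z = √m without correction.

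| Case | m | no continuity correction | with correction |
|---|---|---|---|
| untied | 5 | z = 7.5/3.708 = 2.023, p = 0.043 | z = 7.0/3.708 = 1.888, p = 0.059 |
| untied | 6 | z = 10.5/4.770 = 2.201, p = 0.028 | z = 10.0/4.770 = 2.097, p = 0.036 |
| all tied | 4 | z = 2.000, p = 0.046 | z = 4.5/2.5 = 1.800, p = 0.072 |
| all tied | 5 | z = 2.236, p = 0.025 | z = 7.0/3.354 = 2.087, p = 0.037 |

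Without correction, p falls below 0.05 from m = 5 (untied) or m = 4 (all tied). With it, the thresholds are 6 and 5. The exact figures are unaffected.

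*Baseline hours unrecorded.* There are no complete pairs, so no p-value exists.

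*Some patients wore a sleeve before.* Differences can then be negative, the formula above no longer applies, and the test can be run. It would compare wear before the study with wear during it, which is still not change over follow-up.

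**Reading 2: baseline governs PROMs only.** The sentence names three follow-up times, which form 3 × 2 / 2 = 3 possible pairs. It does not say which call is the reference, or that all three pairs are to be tested. Patient Assessment does not say at which contacts usage is asked, so it is not certain that all three pairs will exist.

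**The case against.** The best defence is that nobody intended a baseline test of hours. Usage is collected alongside satisfaction and complaints, which make sense only after wear, so the second reading is plausible and the zero-baseline arithmetic describes a test that may never be run. That is fair, and it is why the arithmetic is offered only for one branch. It does not rescue the sentence, whose natural grammar makes baseline the comparator for both items; the alternative reading leaves the reference unnamed.

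Two further points limit the claim. A reader might infer that the baseline test must fail. The documents do not support that, because the eligibility criteria do not rule out earlier sleeve use. A reader might also infer that the follow-up calls are unspecified. They are named; what is missing is the reference among them and the times at which usage is asked.

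Finally, the consequence is small. No decision rule rests on this test. That stands, and it sets the weight of the point.

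**Conclusion.** The point holds as a minor one. The stated rule for hours of sleeve use is faulty as written, and incomplete on the more charitable reading. If there was no earlier wear and baseline hours are set to zero, the exact test is significant at 0.05 whenever six or more patients report any use. This assumes two-sided testing and the usual dropping of zero differences. If baseline hours were not recorded, the test cannot be run. If baseline was meant for PROMs only, a reference call has to be named.

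It would be tempting to conclude that the sleeve's effect on PROMs is compromised. The documents give no basis for that here: the PROM comparisons with baseline are defined on either reading, and they carry the stated objective. Only the adherence analysis is affected.

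**What to change.** Split the sentence in the Statistical Analysis section and add the missing collection times:

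- Limit the signed-rank comparison with baseline to PROMs.
- In Patient Assessment, state that usage is asked at 2 weeks, 6 weeks and 3 months, or at which of these it was asked.
- Summarise average daily hours at each call: number answering, number reporting none, median and interquartile range.
- If change in wear is to be tested, name the reference call. One option is 6 weeks and 3 months, each against 2 weeks, by paired signed-rank test in patients who answered at both calls, described as descriptive and unadjusted for multiplicity. The documents do not dictate the 2-week reference; all three pairs, or the summary alone, would also be coherent.
- If normal-approximation p-values are reported, say whether a continuity correction is used.

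The document is dated April 2022, while under Patient Recruitment and Inclusion "the authors will prospectively follow a series of patients at an outpatient orthopaedic sports medicine clinic between February and July 2021". If the change is made after data collection, label it post hoc.

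The cost is a few lines of text, with no new visits or instruments. In the option above, two paired comparisons replace three against baseline. The drawback is that paired tests use only patients who answered at both calls, so those who stopped wearing the sleeve and missed calls may be under-represented. Power is also low in a small cohort: when all changes go one way, five changed patients give p = 2 × 0.5^5 = 0.0625 and six give 0.031, so at least six must change for exact p < 0.05. The summary should therefore be the main output. If usage was not asked at every call, only the summary and whatever pair exists remain.

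### The test across the four time points is Kruskal-Wallis, which is for independent groups, but the scores are repeated measures on the same patients; with positive within-patient correlation its p-values are too large.

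*Combined protocol and SAP*

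**What the plan says.** Under Patient Recruitment and Inclusion, the investigators "will prospectively follow a series of patients at an outpatient orthopaedic sports medicine clinic between February and July 2021". There is no comparison arm. Under Patient Assessment, the outcome questionnaires are repeated in those patients: "These surveys will be administered at the initial visit and subsequently over the phone at 2 weeks, 6 weeks, and 3 months later".

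The Statistical Analysis section then gives three rules for these scores, one after another:

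- Follow-up against baseline: "Wilcoxon Signed-Rank test will be used to compare baseline PROMs" with each later visit. This is a paired test.
- All four visits together: "Kruskal Wallis test will be performed to evaluate differences in PROs between the four time points".
- Unequal numbers at different visits: "only patient scores that are available between groups will be analyzed".

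The threshold for all of them is one sentence: "Significance will be set to an alpha of 0.05". No Friedman test, mixed model or other repeated-measures method is named anywhere.

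**The concern.** Kruskal-Wallis takes its reference distribution from independent samples. Here each patient contributes one score to every sample. Stable differences between patients, which a within-patient comparison should remove, stay in the error term. If a patient's scores are positively correlated over time, the statistic is too small and the p-value too large.

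The plan is also inconsistent with itself. The signed-rank rule treats the scores as paired, and the rule on available scores points to matched data. Only the four-visit test ignores the pairing. Restricting it to matched scores would not repair it, because Kruskal-Wallis on matched data still discards the matching.

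The stake is sensitivity in a study that describes its cohort as small. The four-visit test may miss real change, or be non-significant for a questionnaire whose signed-rank test is significant. The plan does not say how to read that conflict.

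**Working it through.** **Inputs.** From the documents: one patient series, four assessments per patient, alpha 0.05. The documents state no sample size, effect size, standard deviation or within-patient correlation, so there is no figure of the plan's to reproduce except the nominal 5%. Everything else below is assumed.

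**Step 1: true level, by formula.** With four time points, no change, and a common within-patient rank correlation r, the Kruskal-Wallis statistic is distributed approximately as (1 − r) × chi-square on 3 degrees of freedom. The 5% critical value is 7.815, so the true level is P(chi-square(3) > 7.815 / (1 − r)):

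- r = 0.3: 7.815 / 0.7 = 11.16, true level 0.011
- r = 0.5: 7.815 / 0.5 = 15.63, true level 0.0014
- r = 0.7: 7.815 / 0.3 = 26.05, true level below 0.0001

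**Step 2: true level, by simulation.** Normal scores at four visits, equal correlation between all visits, n = 20 to 50, 20,000 runs per setting. Kruskal-Wallis rejects in about 1.2%, 0.3% and 0.01% of runs at correlations of 0.3, 0.5 and 0.7. Friedman rejects in 4.6% to 5.0%. At correlation 0 Kruskal-Wallis holds its level (4.9%), so the correlation is the cause.

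**Step 3: power and conflict.** Same model, n = 30, shift of 0.4 SD at all three follow-ups. The last two columns give the chance that the 3-month signed-rank test is significant and the four-visit test is not.

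| Correlation | Kruskal-Wallis power | Friedman power | Signed-rank power, 3 months vs baseline | Conflict, Kruskal-Wallis | Conflict, Friedman |
|---|---|---|---|---|---|
| 0.3 | 22% | 34% | 42% | 24% | 17% |
| 0.5 | 16% | 46% | 55% | 40% | 18% |
| 0.7 | 9% | 69% | 77% | 67% | 15% |

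**Step 4: sensitivity to the assumptions.**

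- *Larger effect (0.8 SD, n = 30).* Kruskal-Wallis / Friedman power is 89/91%, 91/98% and 94/>99.9% at the three correlations.
- *Correlation that decays between visits* (first-order autoregressive, visits treated as equally spaced, n = 30, 0.4 SD). Power is about 25/28%, 21/34% and 15/49% at lag-one correlations of 0.3, 0.5 and 0.7. Kruskal-Wallis still falls below its nominal level: 0.2% to 0.3% at 0.7, for n = 20 and 30.
- *Missed visits* (n = 30, 0.4 SD, scores missing completely at random). With 10% missing at each phone visit, 30 × 0.9³ ≈ 22 patients are complete. Friedman on complete patients against Kruskal-Wallis on every available score gives 52% vs 10% at correlation 0.7, but 24% vs 21% at 0.3. With 15% missing and correlation 0.3 there is no gain (20% vs 21%).
- *Zero or negative correlation.* At 0, Kruskal-Wallis is slightly more powerful (29% vs 24% at n = 30, 0.4 SD). At −0.2 it is slightly liberal (true level 6.3% to 7.9%, n = 20 and 40).

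**The case against.** The strongest reply is that little depends on this test. The plan does not make the signed-rank comparisons conditional on it, those comparisons are valid as written, and the error does not favour the sleeve. That stands, and it limits the seriousness of the point. It does not make the test fit the design.

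Second, the direction requires positive correlation, which the documents do not state. That is true, but positive correlation is the expected case when one patient repeats one questionnaire over three months.

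Third, equal correlation between visits flatters Friedman. This also stands in part. With decaying correlation the power gap narrows, and at 0.8 SD with lag-one correlation 0.3 Kruskal-Wallis is slightly ahead (87% vs 84%). The fall below the nominal level remains.

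Fourth, the missing-data comparison gives Kruskal-Wallis every available score, whereas the plan's own rule may mean matched scores only. The rule is ambiguous. On the matched reading Kruskal-Wallis does worse (about 9% and 5% power at correlations of 0.5 and 0.7 with 10% missing per visit), so this objection strengthens the point.

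Fifth, Friedman does not remove the conflict with the signed-rank tests, which still occurs in 15% to 18% of cases in the table, and a repeated-measures model on all scores could equally be the main test. Both remarks are fair. What is required is a method that respects the pairing; Friedman is the one closest to the rank-based plan.

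**Conclusion.** The point holds. An independent-samples test is specified for repeated scores from the same patients, and nothing else in the document corrects it. Given positive within-patient correlation, the p-values are too large and the four-visit test runs well below its stated 5% level. The loss of power ranges from negligible (large effect, or low correlation with many missed visits) to severe (9% against 69% at n = 30, 0.4 SD, correlation 0.7). Where the study falls in that range cannot be settled from the documents. The mismatch between test and design does not depend on these assumptions; only its size does. It should be fixed, but it does not invalidate the planned comparisons with baseline or create a spurious finding of benefit.

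**What to change.** Replace the Kruskal-Wallis sentence with wording such as:

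> Differences in each PROM across the four time points will be tested with the Friedman test in patients with scores at all four time points.

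Keep the signed-rank comparisons with baseline, and add:

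> As a sensitivity analysis, a repeated-measures mixed model with visit as a fixed effect and patient as a random effect will use all available scores.

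Also say in one sentence whether the signed-rank comparisons depend on the four-visit result, since disagreement remains possible with any such test.

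The cost is a few sentences and no new data. The drawback is that Friedman drops anyone who misses a phone visit; the mixed model covers those patients. The document is dated April 2022 and the clinic window is February to July 2021, so follow-up data may already have been in hand. The change should therefore carry its date and state whether it was made before or after access to those data.

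### Eighteen planned PROM comparisons each use an unadjusted 0.05, and this document gives no primary outcome, testing order, adjustment or exploratory label

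*Combined protocol and SAP*

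**What the plan says.** Under Patient Assessment, six instruments are listed (UCLA, LKS, OKS, KOOS, SANE and VAS), introduced by "Participants will be asked to complete the following patient reported outcome measures (PROM". On timing: "These surveys will be administered at the initial visit and subsequently over the phone at 2 weeks, 6 weeks, and 3 months later". Under Statistical Analysis, the paired comparison is "Wilcoxon Signed-Rank test will be used to compare baseline PROMs and hours of sleeve use with those at 2 week, 6 week, and 3 month". A Kruskal-Wallis test across the four time points is also planned, but it is not described as a gate for the paired tests. The decision rule is "Significance will be set to an alpha of 0.05".

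The Objectives section sets the aim as to "investigate the effect of a bioactive sleeve on patient reported outcome measures (PROMs) in a small cohort of OA patients", which names the PROMs as a group. Neither the Objectives, the Methods nor the Statistical Analysis section singles out one PROM or one visit, orders the tests, adjusts for their number or calls them exploratory. Sidedness, sample size and correlations are not stated.

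**The concern.** The background says that the literature on "their efficacy for relieving pain and improving function in the setting of knee OA is limited", so the error that matters most is a false benefit on some PROM at some visit. Under the text as written, any one of the 18 tests reaching 0.05 may be declared significant, and the plan does not say which results carry the conclusion. The risk is selective emphasis: all 18 comparisons are planned, but a report could lead with the few that came out significant and present them as if each had been the single question at 0.05.

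**Working it through.** **The plan's own figure.** The 0.05 is a setting and not a derived quantity, so there is nothing to reproduce. For one two-sided test under no change, it means 5% for any significant result and 2.5% for a false benefit. Two-sided testing is assumed.

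**Inputs from the document.** 6 PROMs × 3 follow-ups = 18 tests, each at 0.05. KOOS is counted as one score. The Kruskal-Wallis, Mann-Whitney and hours-of-use tests are left out, so 18 is a low count.

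**Inputs assumed.** n = 30 (20 and 40 also run), normal data, no true change on any PROM at any visit, and correlation between PROMs from 0 to 0.9.

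**Expected count under no change.** 18 × 0.05 = 0.9 significant tests, of which 18 × 0.025 = 0.45 are false benefits. This holds whatever the correlations.

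**Independence, for reference only.** Any significant result: 1 − 0.95^18 = 60.3%. At least one false benefit: 1 − 0.975^18 = 36.6%. The design cannot be assumed to reach these values, because the three changes on a PROM share one baseline and the six PROMs come from the same patient.

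**Correlation between two changes from the same baseline.** With equal variances, baseline-to-follow-up correlation b and follow-up-to-follow-up correlation f, it is (1 − 2b + f) / (2(1 − b)).
- If all visits are equally correlated (f = b), it is 0.5 whatever the value of b.
- If b = 0.5 and f = 0.9, it is (1 − 1 + 0.9) / 1 = 0.9. This case is plausible because baseline is taken in clinic and the follow-ups by telephone.

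**Simulated chance of at least one false benefit / any significant result:**

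| PROM correlation | Changes correlated 0.5 (exact signed-rank, n = 30, 100,000 runs) | Changes correlated 0.9 (normal limit, 150,000 runs) |
|---|---|---|
| 0 | 32.6% / 55.7% | 22.4% / 40.6% |
| 0.5 | 24.2% / 46.8% | 16.0% / 32.3% |
| 0.7 | 19.8% / 38.9% | 12.9% / 25.7% |
| 0.9 | 13.6% / 27.1% | 8.7% / 17.3% |

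Autoregressive visits (0.6 or 0.8) and the random-walk limit fall between the table's extremes. The random-walk limit, for example, gives 28.8% / 50.2% at PROM correlation 0 and 11.9% / 23.6% at 0.9. Over n = 20, 30 and 40, the highest values in the shared-baseline model are 32.8% and 55.7%. The overall ranges are therefore about 9-33% and 17-56%. At PROM correlation 0.5-0.7 they are about 13-24% and 26-47%.

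**If some PROMs truly improve.** In the equal-visit, autoregressive and random-walk models, the chance of a false benefit among the remaining null tests is 11-28% when one PROM improves (15 tests left) and 9-18% when three do (9 tests left).

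**Effect of Holm across 18.** Under no change, with equally correlated visits and n = 30, the chance of any significant result falls to 4.7% at PROM correlation 0 and 2.4% at 0.9. The chance of a false benefit falls to 2.4% and 1.2%.

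**The case against.** The strongest reply is that this is an uncontrolled series in a small cohort, so the missing control group limits any conclusion about the sleeve more than multiplicity does. No change on all six PROMs is a reference case, since natural change or regression to the mean could move them. That stands, and it favours a simple exploratory label as a proportionate remedy. It does not make an unqualified 0.05 across 18 tests acceptable, because the plan still lets any of them be declared significant.

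A second reply is that the ranges rest on assumed correlations. This also stands. The upper end needs nearly uncorrelated PROMs, which is unlikely for overlapping knee scores in one patient. Nor are the ends limits: if all 18 statistics had a common correlation of only 0.1, any significant result would reach 58.9%. Only the size is uncertain, because every setting run stayed above 2.5% and 5%.

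A reader might infer three stronger things that the documents do not support.
- That the trial has no primary outcome. The Methods place ClinicalTrials.gov registration before follow-up, and that record is not part of the documents, so the absence is shown for this document only.
- That comparisons were picked after the fact. All 18 are prespecified in the Statistical Analysis section.
- That the analysis was written with outcome data in hand. The document is dated April 2022 and says the investigators "will prospectively follow a series of patients at an outpatient orthopaedic sports medicine clinic between February and July 2021", but it does not say whether data had been seen.

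**Conclusion.** The point holds for this document and should be fixed. The stated 0.05 does not protect a conclusion drawn from whichever of 18 tests is significant. At moderate PROM correlations, the chance of at least one false benefit is about 5 to 10 times the single-test figure (13/2.5 = 5.2; 24/2.5 = 9.6). Even with correlations of 0.9 among both PROMs and changes, it is more than three times that figure (8.7/2.5 = 3.5). These sizes assume two-sided tests, no true change and correlations that the document does not give. The existence of the inflation does not depend on the particular values run; its size does.

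**What to change.** **First, check the registration made before patients were followed.** If it prespecified one PROM at one visit as primary, carry that into the SAP at two-sided 0.05. Treat the other 17 comparisons either as exploratory or as secondary, with Holm applied only if the primary is significant. This can be done whether or not data have been seen, because the choice was made earlier.

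**If it did not, replace the alpha sentence with one of these:**

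(a) *The 18 PROM-by-visit tests are exploratory. All 18 changes will be reported as Hodges-Lehmann estimates with 95% confidence intervals that are not adjusted for multiplicity. No significance will be claimed.*

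(b) *The 18 PROM-by-visit Wilcoxon tests form one family. All 18 changes will be reported as Hodges-Lehmann estimates with unadjusted 95% confidence intervals, and with raw and Holm-adjusted two-sided p-values. Significance will be claimed only where the adjusted p-value is below 0.05. All other tests are exploratory.*

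**In either case, add a sentence saying whether outcome data had been seen when the option was chosen.** Neither option requires choosing among outcomes, but choosing between them after seeing p-values is itself data-dependent.

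**Cost.** The change is to wording only.
- A registered primary keeps its full power (78% for a change of 0.53 SD of the change, at an assumed n of 30). The other 17 tests under gated Holm average 36-44% if all are real at that size.
- Option (a) costs no power but gives up any significance claim.
- Option (b) lowers power for a single real change of 0.53 SD at n = 30 from 78% to about 36%. The loss is similar at n = 20 (0.66 SD) and n = 40 (0.45 SD). If all 18 changes are real at 0.53 SD, average power at n = 30 is 44-46%.

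The report should also say that no option makes a change attributable to the sleeve without a control group.
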